4.1.3 PK Population

The PK population will include all patients randomized after implementation of Protocol Version 4 who received at least one dose of RO7234292, and had sufficient sampling to permit PK evaluation.

4.2 ANALYSIS OF STUDY CONDUCT

The numbers of patients who enroll in the study, discontinue from the study (during on-treatment period or during off-treatment follow-up period), and complete the study will be summarized overall and by treatment arm. Reasons for premature study withdrawal will be listed and summarized. Enrollment and major protocol deviations will be listed and evaluated for their potential effects on the interpretation of study results. In addition, major protocol deviations that are considered related to Coronavirus Disease 2019(COVID-19) will be listed and summarized descriptively.

4.3 ANALYSIS OF TREATMENT GROUP COMPARABILITY

Demographic and baseline characteristics will be summarized by treatment group using means, standard deviations, medians and ranges for continuous variables and proportions for categorical variables, as appropriate. Summaries will be presented overall and by treatment.

4.4 EFFICACY ANALYSIS

Given the date of the public announcement of the Sponsor halting dosing in Study BN40423 (following the iDMC recommendation), only data collected up to 22 March 2021 will be used to evaluate the efficacy of RO7234292 (to avoid any bias from data collected after the official announcement).

For all efficacy endpoints, the baseline will be defined as the last assessment on Day 1. Further reporting windows are defined in [Appendix 1](#).

4.4.1 Covariate Adjustment

Unless otherwise noted, analyses of efficacy endpoints (primary, secondary, and exploratory) will include the following covariates in the model:

- Treatment: Placebo, RO7234292 Q8W, and RO7234292 Q16W
- CAG at baseline
- CAG-Age Product (CAP) at baseline (defined as $(CAG-33.66)*age$)
- Age at baseline

For continuous endpoint the baseline of the endpoint will also be included in the model unless stated otherwise.

4.4.2 Primary Efficacy Endpoint

The primary efficacy objective for this study is to evaluate the efficacy of RO7234292 compared with placebo on the basis of cUHDRS score.

Following the iDMC recommendation and Sponsor's decision to discontinue study treatment in this study, as of 22 March 2021, the primary estimand as described in Protocol Section 6.6.1 and the planned analysis method as described in Protocol Section 6.6.2 will not be considered for the analysis of the primary efficacy endpoint.

Instead of analysis of variance (ANCOVA) as planned per protocol, the primary efficacy endpoint will be evaluated by means of a Mixed Model Repeated Measurements (MMRM) analysis using the covariates described in Section 4.4.1 as fixed effects. The model will also include visit (as a categorical factor) and visit-by-treatment interaction. An unstructured (UN) variance-covariance structure will be applied to model the within patients' errors; if the model fails to converge, the following variance-covariance structures will be tested as alternatives in the pre-specified order: Heterogeneous Toeplitz (TOEPH), Antedependence (ANTE[1]) and Heterogeneous Compound Symmetry (CSH). On the basis of this analysis, least squares means for the treatment differences at Week 69 and corresponding 95% confidence intervals (CIs) will be derived. Unlike as planned per protocol, no adjustments for multiple comparisons will be incorporated into the analyses.

The MMRM analysis is equivalent to a 'hypothetical' strategy, estimating the treatment effect as if patients would have fully adhered to their intended treatment regimen. This hypothetical strategy is generally considered, but actual off-treatment values assessed after treatment discontinuation before 22 March 2021 are included in the analysis. Missing values (because no data was collected) will not be imputed but will be handled via the MMRM. The MMRM assumes that missing data are missing at random (MAR). That is, MMRM assumes that given the statistical model and given the observed values of the endpoint, missing data are independent of the unobserved values (O'Kelly and Ratitch 2014).

The primary endpoint will also be summarized using descriptive statistics.

4.4.3 Secondary Efficacy Endpoints

The continuous secondary efficacy endpoints will be analyzed via an MMRM as described in Section [4.4.2](#).

Similar as for the primary endpoint, the MMRM analysis will be performed instead of per protocol planned analyses via ANCOVA. For these analyses, least squares means for the treatment differences at Week 69 and corresponding 95% CIs will be reported. No adjustments for multiple comparisons will be incorporated into the analyses, especially the testing strategy described in Protocol Section 6.3 is not considered for any analyses.

Change from baseline at Week 69 will be analyzed for the following secondary endpoints:

- TFC
- TMS
- SDMT
- SWR Test
- CGI-S

The categorical secondary endpoints will be analyzed descriptively and by means of logistic regression including treatment (categorical), CAG repeat length, and CAP score as covariates.

- Analyses will be conducted for the following categorical secondary endpoints:
Proportion of patients with a decrease from baseline of at least 1 point on the TFC at Week 53 and at Week 69
- Proportion of patients with a decline from baseline of at least 1.2 points on the cUHDRS at Week 53 and at Week 69
- Proportion of patients with an unchanged or improved score on the CGI-C score from baseline at Week 53 and at Week 69

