2.2 ENDPOINTS

Following the iDMC recommendation and Sponsor's decision to discontinue study treatment in this study, as of 22 March 2021, only data collected up to 22 March 2021 will be used to evaluate the efficacy of RO7234292. By that date, approximately 80% of the participants reached their Week 69 visit, therefore the efficacy and biomarker outcome measures will be evaluated based on change from baseline at Week 69 (rather than change from baseline at Week 101).

However, all outcome measures are listed below as planned per protocol (i.e., referring to change from baseline at Week 101).

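### The TFC and cUHDRS responder models omit the baseline score and, as specified, make no use of earlier visits when status is missing, which gives up precision that the MMRM of the same scales keeps

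*SAP*

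**What the plan says.** Section 4.4.3 (SAP Version 3) analyses the categorical secondary endpoints descriptively and "by means of logistic regression including treatment (categorical), CAG repeat length, and CAP score as covariates". Two of them are cut-points on scales that are also analysed continuously: TFC down by at least 1 point and cUHDRS down by at least 1.2 points, each at Weeks 53 and 69.

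Section 4.4.1 sets the general rule: "Unless otherwise noted, analyses of efficacy endpoints (primary, secondary, and exploratory) will include the following covariates in the model", followed by treatment, CAG, CAP and age. It adds: "For continuous endpoint the baseline of the endpoint will also be included in the model unless stated otherwise". The MMRM for continuous TFC and cUHDRS therefore carries baseline score and age; the logistic models carry neither.

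On missing data, Section 4.4.2 states: "Missing values (because no data was collected) will not be imputed but will be handled via the MMRM". That sentence belongs to the MMRM. Section 4.4.3 gives no rule for a patient without a responder status and no denominator for the proportions. Section 4.4 restricts the evidence: "only data collected up to 22 March 2021 will be used to evaluate the efficacy of RO7234292". Section 2.2 reports that "approximately 80% of the participants reached their Week 69 visit" by that date. Appendix 1 maps early-termination and unscheduled UHDRS and CGI-C assessments to scheduled visits, with a Week 69 window of study days 420 to 531. Section 3.1 says that randomisation is unstratified.

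**The concern.** Whether a patient crosses a fixed drop on TFC or cUHDRS can be expected to depend on the starting score. Baseline is already collected and already used for the continuous version of each endpoint. Leaving it out of the binary version gives up precision at no saving and, with unstratified allocation, leaves any chance baseline imbalance between arms uncorrected.

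Secondly, a logistic model at one visit cannot borrow from earlier visits as the MMRM does. With no stated rule, the software default is to fit patients who have a value in the window. The continuous and binary analyses of one scale would then rest on different patients and different missing-data assumptions. Counting missing patients as not declined, or keeping all ITT patients in the denominator, would be equally compatible with the text and would give other proportions. Section 1 says that the sponsor was unblinded when dosing stopped, so this choice is better fixed in writing than left to programming.

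**Working it through.** **The plan's own figure.** Section 2.3 claims about 80% power with 267 per arm for TFC at Week 101, two-sided 0.025. Re-running that simulation with the stated means, covariance, missingness and 20 imputations gives about 81.8% (21,500 replicates), so the figure reproduces. The SAP states no responder rates and no responder power; every responder figure below rests on assumed rates.

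**Models side by side.**

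| | MMRM of TFC, cUHDRS | Logistic responder model |
|---|---|---|
| Treatment, CAG, CAP | yes | yes |
| Age | yes | no |
| Baseline score | yes | no |
| Earlier visits if Week 69 is absent | used | not used |

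**Age.** Section 4.4.1 defines CAP = (CAG − 33.66) × age, so age = CAP / (CAG − 33.66), an exact though non-linear function of two covariates already in the model. In an assumed population (CAG about 44, SD 2.8; CAP about 500, SD 60 to 80; CAP above 400; age 25 to 65), a linear regression on CAG and CAP explains about 96% of the variance of age. Omitting age changes little.

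**Baseline score.** The documents give no association between baseline and the chance of crossing the threshold, so the gain from adjustment can be stated in direction only.

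**How many lack Week 69.** 0.20 × 801 = 160.2 patients; 160.2 / 3 = 53.4 per arm; 267 − 53.4 = 213.6, about 214 per arm. Remapped visits may raise this somewhat.

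**Precision.**
- Observed cases against full data: standard-error ratio 1/√0.8 = 1.118.
- MAR analysis using one earlier visit: Section 2.3 gives a correlation of 1.8 / (1.56 × 1.78) = 0.648, about 0.65, for continuous TFC at Weeks 49 and 101. Taking 0.65 as an assumption, the ratio is √((1 − 0.4225)/0.8 + 0.4225) = √1.1444 = 1.070.
- Avoidable part: 1.118 / 1.070 = 1.045, or about 4 to 5%. A stronger Week 53 to 69 correlation would recover more; dichotomising may recover less.
- Total cost of the missing values, for scale: with assumed placebo rates of 30% to 70%, a 12-point difference and two-sided 0.05, power is 80% to 90% at 267 per arm and 70% to 83% at 214. At a 50% placebo rate the 95% half-width goes from 8.4 to 9.3 points. Imputation recovers only part of this.

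**Denominator.** If 50% decline among the observed 80%, the overall rate lies between 0.8 × 50% = 40% and 40% + 20% = 60%. Counting all missing patients as not declined gives 40%.

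**Bias (illustrative).** Assume normal declines with means 0.79 then 1.0 on placebo and 0.47 then 0.6 on active, SDs 1.56 and 1.65, correlation 0.65, and a drop of at least 1 as the event.
- 20% missing at random calendar-wise: the risk difference is 9.6 points in full data and 9.6 in observed cases.
- Missingness depending on the earlier value, strongly on active and weakly on placebo (log-odds slopes 0.8 and 0.1 per SD; 19.4% and 16.8% missing): full data 50.0% v 40.4%, difference 9.6; observed cases 49.5% v 36.7%, difference 12.8. Missingness here depends only on an observed earlier value, which is the situation MAR imputation addresses.

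**The case against.** The plan does nothing that it forbids. Section 4.4.1 asks for baseline only with continuous endpoints, and its opening words allow departures, so the short covariate list is permitted. An unadjusted baseline does not invalidate a randomised comparison. These are secondary endpoints in a halted trial, without multiplicity control, and the same scales have MAR-based MMRM analyses. The protocol, which is not at hand, may hold a rule for missing responder status. All of this stands, and it limits the point to a better method rather than an error.

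Four stronger readings are tempting and unsupported:
- That the SAP discards everyone without a Week 69 value. It never says so; observed-case analysis is the default where no rule is given. Appendix 1 also remaps some visits, and Week 53 is analysed in parallel.
- That the 20% biases the comparison. Not having reached Week 69 by a calendar date depends largely on enrolment date, which randomisation spreads evenly across arms. A worst case in which every dropout is a decliner may be missing not at random, and MAR imputation would not cure it.
- That the full 12% inflation (1.118) can be recovered. Imputation cannot restore uncollected data.
- That dropping age matters materially. CAG and CAP already carry nearly all of it.

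**Conclusion.** The point holds as a weakness of method. The TFC and cUHDRS responder models omit a collected baseline score that the MMRM of the same scales uses, and as specified they cannot use earlier visits of patients without a status. The cost is mainly precision. The avoidable part from missing Week 69 values is about 4 to 5% of the standard error, if the 0.65 correlation carries over, the earlier visit is observed in all of the missing 20%, and that 20% is mostly administrative. The further gain from adjusting for baseline cannot be sized from the documents. Bias needs earlier discontinuation to relate to decline differently by arm. The shift from 9.6 to 12.8 points shows that this could matter under assumed inputs; it is not an estimate for this trial.

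**What to change.** In Section 4.4.3:
- Add baseline TFC to the TFC responder model and baseline cUHDRS to the cUHDRS model. Include age to match Section 4.4.1, expecting little effect. CGI-C has no baseline value of its own, so this change does not extend to it.
- State the denominator and how a missing status is treated.
- Multiply impute the TFC and cUHDRS scores at Weeks 53 and 69 under the MMRM's MAR assumption and covariates, dichotomise, fit the logistic model and pool by Rubin's rules. Do this at least as a sensitivity analysis beside the observed-case fit.
- Report a standardised risk difference with the odds ratio.

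The cost is SAP wording and modest programming. The odds ratio becomes conditional on more covariates and is not directly comparable with the less adjusted one. In a logistic model the benefit of baseline adjustment shows as power and in the standardised risk difference, not as a smaller standard error of the log odds ratio, which is why the risk difference should accompany it. Because the sponsor is unblinded, the amendment should say that the change was made after unblinding.

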4.4.4 Exploratory Efficacy Endpoints

The exploratory efficacy endpoints are listed in Section [2.2.3](#).

The exploratory endpoints will be analyzed via an MMRM as described in Section [4.4.2](#).

Results for the digital endpoints (including HD-SDI, HD-CIAOS, and sensor-based measures collected by the Roche HD mobile) will not be reported in the Clinical Study Report (CSR).

4.4.5 Subgroup Analyses

Subgroup analyses will be performed for the following endpoints:

- Change from baseline in cUHDRS and the individual components (TMS, TFC, SDMT, SWRT) at Week 69
- Change from baseline in CSF NfL protein level at Week 69
- Change from baseline in CSF mHTT protein level at Week 69 (due to data availability, the analyses of CSF mHTT protein level might not be completed by the time of the CSR writing so results of this subgroup analysis may be reported in an addendum to the CSR)
- Annualized percent change from baseline in whole and regional brain (caudate and ventricular) boundary shift integrals (BSI) at Week 69

The thresholds for the categories for each variable were chosen on the basis of median or frequency distribution in the population, thus the definitions of the subgroups actually chosen differ slightly from the definitions as specified in the protocol:

- Sex (male versus [vs.] female)
- Age at baseline (≤ 48 years vs. > 48 years (instead of ≤ 45 years vs. > 45 years as planned per protocol))
- CAG repeat length (≤ 44 vs. > 44 [instead of ≤ 43 vs. > 43 as planned per protocol])
- Stage at baseline (Stage I vs. Stage II-IV [instead of Stage I vs. Stage II vs. Stage III as planned per protocol])

For subgroups defined by 'baseline variables' (e.g., baseline_CAG ≤ 44 vs. baseline_CAG > 44), a similar MMRM as the one described in Section 4.4.2 will be used, with the addition of the following covariates: subgroup (as categorical; the corresponding continuous variable will be excluded from the model if it was considered as a covariate in the original model), visit-by-subgroup interaction, treatment-by-subgroup interaction and visit-by-treatment-by-subgroup interaction.

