In March 2021, following the recommendation from the independent Data Monitoring Committee (iDMC) as a consequence of a regular iDMC safety review, the Sponsor issued an Urgent Safety Measure (USM) to permanently halt the dosing in the BN40423 study and implemented a new protocol amendment (Protocol Version 6). This allowed patients to enter the off-treatment follow-up period, to monitor their safety and efficacy endpoints after the treatment discontinuation. At the same time, the Sponsor has been unblinded, to allow the start of exploratory analyses as soon as possible, for internal decision making on further clinical development of RO7234292.

This SAP will describe the statistical analysis of the efficacy and safety analyses of the cohort enrolled under Protocol Version 4 and onwards. The statistical analysis will be performed on the data collected up to the treatment termination (referred as "on-treatment period" thereafter) and data collected after the treatment termination (referred as "off-treatment follow-up period" thereafter).

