4.4.6 Post-Hoc Exploratory Analysis

Following the recommendation from the iDMC to halt dosing in Study BN40423, the sponsor decided to perform post hoc exploratory analysis in subgroups defined by baseline age and CAP (thresholds defined based on approximate median splits; i.e., Age < 48 and CAP < 500 ; Age ≥ 48 and CAP < 500 ; Age < 48 and CAP ≥ 500 ; and Age ≥ 48 and CAP ≥ 500). A similar MMRM analysis as the one described in Section 4.4.2 was used, with the addition of the following covariates: subgroup (as categorical), visit-by-subgroup interaction, treatment-by-subgroup interaction and visit-by-treatment-by-subgroup interaction. Age and CAP at baseline were removed from the MMRM analysis. Analyses for this subgroup were performed for the endpoints as listed in Section 4.4.5. For these subgroups defined by baseline age and CAP, strata were defined by post-randomization variables (e.g., patients with low or high exposure) and propensity score methodology was used in order to define the right 'control group'.

by assigning weights (defined as $(PS/[1-PS])$, where PS is the propensity score as estimated using a logistic regression) to placebo patients (to balance out potential confounders) and then employing a weighted regression. The standard errors of the fixed-effects parameters were estimated by using the asymptotically consistent and robust estimator (commonly referred to as the “sandwich” estimator, [Liang and Zeger 1986](#)).

Analyses were performed for the treatment group comparisons of Placebo vs. RO7234292 Q16W.

The following strata were considered:

- Strata split by median of average concentration at Week 21
- Strata split by median of average percent change from baseline in mHTT at Week 21 (due to data availability, the analyses of strata by mHTT might not be completed by the time of the CSR writing so results of this analysis may be reported in an addendum to the CSR)

Those analyses will be re-run on the final data after database lock.

In addition, demographic and baseline characteristics will be summarized by subgroups defined by above mentioned baseline age and CAP using means, standard deviations, medians and ranges for continuous variables and proportions for categorical variables, as appropriate.

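### SAP Section 4.4.5 replaces the protocol's age, CAG and stage subgroups with data-derived ones recorded after sponsor unblinding, does not keep the protocol splits, and does not label the new ones post hoc

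*SAP*

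**What the plan says.** Section 4.4.5 gives the rule for the subgroup boundaries: "The thresholds for the categories for each variable were chosen on the basis of median or frequency distribution in the population". It then states the consequence: "thus the definitions of the subgroups actually chosen differ slightly from the definitions as specified in the protocol".

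The four subgroup variables are treated as follows:

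- Age is split at ≤48 against >48, "instead of ≤ 45 years vs. > 45 years as planned per protocol".
- CAG repeat length is split at ≤44 against >44, "instead of ≤ 43 vs. > 43 as planned per protocol".
- Stage is given as "Stage I vs. Stage II-IV [instead of Stage I vs. Stage II vs. Stage III as planned per protocol".
- Sex is given as "Sex (male versus [vs.] female", with no note of any change.

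Section 1 describes the March 2021 dosing halt and says of the sponsor: "At the same time, the Sponsor has been unblinded, to allow the start of exploratory analyses as soon as possible". Section 4.4.6 says that after the halt "the sponsor decided to perform post hoc exploratory analysis in subgroups defined by baseline age and CAP". Its cuts are age 48 and CAP 500, described as approximate median splits.

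**The concern.** A subgroup boundary fixed before anyone has seen outcomes by arm cannot have been shaped by those outcomes. That protection matters more here than usual, because Sections 4.4.2 and 4.4.3 drop all multiplicity adjustment and Section 1 says the unblinded analyses serve decisions on further development.

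The halt explains the move to Week 69 and the data cut-off of 22 March 2021. It does not explain new cuts for age or CAG. A better-balanced split is a good reason to add a boundary, but not a reason to stop reporting the one set beforehand. Section 4.4.6 is openly labelled post hoc. Section 4.4.5 carries no such label, although its boundaries also come from the trial's own data, so a reader of the report could take them for the pre-specified subgroups.

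**Working it through.** **Order of events.**

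1. Dosing halt, data cut-off and public announcement: 22 March 2021 (Sections 2.2 and 4.4). Section 1 places the sponsor's unblinding at the time of the March 2021 halt and the resulting amendment, without giving a day.
2. SAP Version 1 (16 December 2019) states that it covers the Original Design Cohort only, so it fixed no boundaries for this cohort.
3. SAP Version 2, the first to cover this cohort, is dated 1 April 2022: 365 + 10 = 375 days after 22 March 2021.
4. SAP Version 3, the text at hand, is dated 12 May 2022: 375 + 41 = 416 days after.
5. Section 4.4.6 uses the past tense for the age-by-CAP model and says that it was applied to the endpoints listed in Section 4.4.5 and will be re-run after database lock. Treatment comparisons with an age-48 split, crossed with CAP, therefore existed when this text was written.

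**Protocol definition against SAP definition** (the protocol side is known only from the SAP's own notes):

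| Variable | Protocol | Section 4.4.5 | Pre-specified result left? |
|---|---|---|---|
| Age | ≤45 / >45 | ≤48 / >48 | No |
| CAG | ≤43 / >43 | ≤44 / >44 | No |
| Stage | I / II / III | I / II-IV | Stage I only |
| Sex | no change noted | male / female | Yes |

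No section keeps the protocol splits as a further analysis. Section 2 says that the SAP takes precedence over the protocol, so they do not survive by default.

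**How many patients change group (illustration).** The SAP gives no age or CAG distribution, so the spread is assumed. Take whole-year ages from a normal distribution centred at 48.5 with SD s, truncated to 24.5–65.5. The age range of 25 to 65 is from the Protocol Version 3 synopsis in Appendix 1 of SAP Version 1 and is assumed to apply here.

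F(x) = [Φ((x − 48.5)/s) − Φ((24.5 − 48.5)/s)] / [Φ((65.5 − 48.5)/s) − Φ((24.5 − 48.5)/s)]

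Share moved = F(48.5) − F(45.5), that is, patients aged 46 to 48. Counts use the planned 801 patients and the unrounded shares.

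- s = 8: 0.508 − 0.359 = 0.149, about 119 patients
- s = 10: 0.519 − 0.395 = 0.124, about 100 patients
- s = 12: 0.531 − 0.421 = 0.110, about 88 patients

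For CAG, every patient with exactly 44 repeats moves. If that share is 10% to 25% (assumed), this is 801 × 0.10 = 80 to 801 × 0.25 = 200 patients.

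These figures measure movement between groups, not bias.

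**The case against.** The stated rule uses the median or frequency distribution of baseline variables, not outcomes, and a median leaves little room to tune a boundary. Every new cut is printed beside the one it replaces, so the change itself is open. Sections 4.4.5 and 4.4.6 both appeal to medians, so a shared value of 48 is what one population would give. The groups are not even identical: a patient aged exactly 48 is in the lower group in Section 4.4.5 (≤48) and in the upper group in Section 4.4.6 (≥48). CAG and stage are not subgroup variables in Section 4.4.6 at all. Pooling stages may simply reflect small cells.

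All of this stands, and it rules out a stronger reading. A reader might infer that the boundaries were picked because they showed an effect, or might attach an inflated false-positive rate to the subgroup results. The documents support neither. They describe no choice among cut-points by result, and Section 4.4.5 specifies interaction terms but no interaction test at a stated level, so no controlled error rate exists to be inflated.

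The objection does not reach the loss of the protocol splits. The rule offers two bases, median or frequency, without saying which was used for which variable. The SAP does not say when the choice was made, or whether those who made it had seen outcomes by arm. Disclosing the new values does not disclose that timing.

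**Conclusion.** The point holds in a limited form. For age, for CAG repeat length, and for Stages II and III separately, the SAP leaves no subgroup result based on the protocol's definitions. It presents boundaries first recorded more than a year after the March 2021 halt without marking them as such. Sex and the Stage I stratum are unaffected, and so is the main efficacy analysis.

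Outcome-driven selection is not shown; it cannot be excluded from what is written. About 11% to 15% of patients would change age group under the assumed SDs of 8 to 12 years.

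The conclusion rests on two inferences. The date of the choice is inferred from the SAP dates, which show when the cuts were recorded rather than when they were decided. The protocol definitions are taken from the SAP's notes, so whether the protocol allowed distribution-based revision could not be checked.

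**What to change.** In Section 4.4.5, run the protocol splits (age ≤45 / >45, CAG ≤43 / >43, Stage I / II / III) in the same MMRM and name them the pre-specified subgroup analysis. Show sparse stage cells, and any Stage IV patients, descriptively.

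Keep the ≤48, ≤44 and Stage I against II-IV splits beside them, labelled as defined after sponsor unblinding. Add a sentence saying when and by whom they were chosen, and whether outcomes by arm were known at the time.

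The cost is a few extra model runs and forest-plot rows with existing code. No new data are needed.
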